## 5.6 Unscheduled Visit

An unscheduled visit may be performed at any time during the study at the subject's request or as deemed necessary by the PI. The date and reason for the unscheduled visit will be recorded within the eCRF. AE monitoring and concomitant medication recording will be performed by the PI. Other procedures and evaluations will be completed as deemed necessary by the PI and may include (but are not limited to) laboratory safety tests, vital signs and PE.

## 5.7 General Instructions before Study Drug Administration

The following instructions should be followed before AGI-134 administration:

- AGI-134 should only be administered when personnel and therapies are immediately
  available for the treatment of hypersensitivity reactions, should they occur. This should
  include having an open IV cannula and fluid therapy readily available.
- Hypovolaemia, if present, should be corrected prior to administration of AGI 134 according to the study site standard of care.
- For patients who receive routine anti-hypertensive medication, these medications should be withheld in the 24 hours prior to injection of AGI-134.

In patients who experienced a systemic injection related reaction:

 Premedication with an antihistamine is required prior to all subsequent study drug administrations. Premedication should be given 30-45 minutes prior to study drug

agalin A subsidiary of Bio	nnune DLINERX	PRIVILEGED & CONFIDENTIAL
Investigational Product: AGI-134		Protocol No. AGI-134.FIM.101
Phase: I/IIa	doses of AGI-134 in unresectable/metastatic solid tumours.	Version 6.1 31 May 2021

administration if premedication is given orally, or ~15 minutes prior to study drug administration if premedication is given IV.

The time of administration of premedication is to be recorded on site documentation and in the CRF.

The recommended premedication regimen is:

- o H1 blocker (e.g diphenhydramine, promethazine, ceterizine)
- o and H2 blocker (e.g. famotidine).
- Steroids such as dexamethasone should be avoided as premedication; however, short-acting ones may be used to treat injection reactions as needed.

## 5.8 Safety Assessments

Safety assessments will be based on changes from Baseline visit of clinical signs and symptoms reported by the subject or observed by the PI, including AEs, concomitant medication use, treatment compliance, tolerability (e.g. dropouts due to AEs), vital signs, ECGs, PE and laboratory safety assessments.

## 5.8.1 Adverse Events

Adverse Events (AE) will be Reported from the time of informed consent signature and up to 30 days after the last dose of study drug or until the initiation of new anti-cancer treatment, whichever is sooner. SAEs will be recorded up to 90 days following the last dose of study drug or until the subject initiates new anti-cancer therapy, whichever is sooner. Any new AE that occurs between scheduled assessment visits should be brought to the attention of the PI and recorded in the Subject's medical file and on the appropriate eCRF page.

AEs will be reported and graded in accordance with the latest National Cancer Institute Common Terminology Criteria for Adverse Events (NCI-CTCAE) version (currently version 5.0) and coded by Data Management using the latest version of Medical Dictionary for Regulatory Activities (MedDRA, version 24.0; see Section 7.1 for more details).

#### 5.8.2 Concomitant Medication

Review of prior medication (up to one year) and concomitant medications use will be recorded from Baseline visit through all study visits.

#### 5.8.3 Vital Signs, Height and Weight

- Vital signs will be measured once at Screening and once at Termination/Early Termination visit.
- On Cycle 1 Day 1 and Cycle 3 Day 1 will be measured up to 1 hour pre-AGI-134 administration and 0.5, 1, 24, 36, 48 and 72 hrs post dose.
- On Cycle 2 Day 1 and Cycle 4 Day 1 will be measured pre-dose and 2 hours post dose.

agalin A subsidiary of Bio	nnune DLINERX	PRIVILEGED & CONFIDENTIAL
Investigational Product: AGI-134		Protocol No. AGI-134.FIM.101
Phase: I/IIa	doses of AGI-134 in unresectable/metastatic solid tumours.	Version 6.1 31 May 2021

Vital signs will include blood pressure, pulse, oral temperature, O2 saturation and respiration rate following a minimum of 5 minutes rest and prior to blood collection as per standard practice at the investigational site. Significant findings noticed after investigational product administration which meet the definition of an AE must be recorded on the AE eCRF module.

Height and weight will be recorded at Screening. Weight will be recorded at Termination/Early Termination visit as well.

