## Safety Analysis:

Changes in vital signs and routine laboratory data will be presented with descriptive statistics to demonstrate the trend of change.

Number of subjects with physical abnormality at each scheduled visit will be tabulated by body system and by dose level. ECG examination results will be displayed in descriptive statistics and by dose level with number of subjects with abnormal findings tabulated for each schedule visit.

AE incidence will be summarised descriptively by system organ class (SOC), high level term (HLT) and preferred term (PT) using the latest version of Medical Dictionary for Regulatory Activities (MedDRA; current version 24.0) and by dose level and for the total population. The AEs severity grade, as determined by the latest version of the National Cancer Institute Common Terminology Criteria for Adverse Events (NCI-CTCAE; current version 5.0), and their relationship to study drug will be analysed by SOC, HLT and preferred term by dose level and for all subjects as a group. The action taken, and the outcome will also be analysed accordingly.

263		PRIVILEGED & CONFIDENTIAL
Investigational Product: AGI-134	A Phase I/IIa, multicentre, two-parts, open label study designed to evaluate the safety and tolerability of escalating	Protocol No. AGI-134.FIM.101
Phase: I/IIa	doses of AGI-134 in unresectable/metastatic solid tumours.	Version 6.1 31 May 2021

Statistical Analysis
-------------------------

10		PRIVILEGED & CONFIDENTIAL
Investigational Product: AGI-134	A Phase I/IIa, multicentre, two-parts, open label study designed to evaluate the safety and tolerability of escalating	Protocol No. AGI-134.FIM.101
Phase: I/IIa		Version 6.1 31 May 2021

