#### ECG assessment:

- A 12-lead ECG Holter recording device will be connected to the subject 1-2 hours prior to AGI-134 administration and record ECG consecutively for at least 24 hours post AGI-134 administration.
- ECG printouts for safety assessment will be extracted prior to AGI-134 administration (up to 1 hour before dose) and 2 hours post dose (± 30 minutes).
- Symptom-directed physical examination pre-dose only
- Examination of injection- site will be performed 1 hour (±30 min) pre-AGI-134 administration, 1 hour (±30 min)
- Vital signs will be performed up to 1 hour pre-AGI-134 administration and 0.5, 1, 24, 36, 48 and 72 hrs post AGI-134 administration.
- ECOG performance status
- Photography of superficial injected and non-injected lesions will be performed 1 hour pre-AGI-134 administration (±30 min), 1 hour (±30 min)
- Review general instructions before study drug administration (see section 5.7)
- AGI-134 administration on Day 1
- Blood will be drawn for:
  - o CH50 pre-dose
  - o C5a pre-dose, 2 and 6 hours post AGI-134 administration
  - o Flow cytometry pre-dose and 24 hours post AGI-134 administration
  - O Cytokines pre-dose, 2, 6, 12 and 24 hours post AGI-134 administration
  - Anti-Gal antibodies IgG/IgM and sub classing pre-dose
  - PBMC isolation + cryopreservation pre-dose
  - Human leukocyte antigen (HLA) and MHCII haplotyping pre-dose
  - DNA isolation (MSI/dMMR/TMB, WES) pre-dose
  - TCR Sequencing pre-dose
  - RNA isolation (Gene expression/sequencing) pre-dose
  - PK of AGI-134 and metabolites: up to 1 hour prior to AGI-134 administration and at 0.5, 1, 2, 4, 6, 8, 12, 24, 36, 48 and 72 hrs post AGI-134 administration.
     For detailed time window for sample collection refer to the Laboratory Manual.

## 5.3.2 Cycle 1 - Day 3

- Blood will be drawn for:
  - o CBC with differential 48-72 hrs post AGI-134 administration
  - o Biochemistry Panel 48-72 hrs post AGI-134 administration
  - Cytokines: 48hrs post AGI-134 administration
  - RNA isolation (Gene expression/sequencing) 48±24hrs post AGI-134 administration
  - o PBMC isolation + cryopreservation: 48 ±24 hrs post AGI-134 administration

agalin A subsidiary of Bio	nnune DLINERX	PRIVILEGED & CONFIDENTIAL
Investigational Product: AGI-134		Protocol No. AGI-134.FIM.101
Phase: I/IIa		Version 6.1 31 May 2021

- Photography of superficial injected lesions prior to tumour tissue biopsy, if applicable
- Examination of injection prior to tumour tissue biopsy, if applicable

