- Tumour tissue biopsy will be performed 48 ±24 hrs post AGI-134 administration, from injected lesions only. This biopsy is mandatory for superficial injected lesion and is also requested for deep lesions, unless it is not considered in the best interest for the patient by the PI.

## 5.3.3 Cycle 1 - Day 8 and Day 15

The following procedures will be performed:

- Review of change in concomitant medication
- AE Recordings
- Symptom-directed physical examination
- Examination of injection site
- Photography of superficial injected and non-injected lesions if applicable
- Vital signs (blood pressures, pulse rate, O2 saturation, oral temperature in °C, respiratory rate)
- Blood will be drawn for:
  - CBC with differential
  - Biochemistry panel
  - o Anti-Gal antibodies IgG/IgM (Cycle 1 Day 8 only)

## 5.3.4 Cycles 2, 3 and 4

AGI-134 will be administered on Day 1 of each cycle. The following procedures will be performed during these visits; each assessment should be performed before administration of the investigational product unless otherwise specified. Detailed activities are presented in the SoA (APPENDIX A).

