## **Cycle 3 Procedures**

- · Review concomitant medications
- AE Recording
- ECG assessment:
  - A 12-lead ECG Holter recording device will be connected to the subject 1-2 hours prior to AGI-134 administration and record ECG consecutively for at least 24 hours post AGI-134 administration.
  - o ECG printouts for safety assessment will be extracted prior to AGI-134 administration (up to 1 hour before dose) and 2 hours post dose (± 30 minutes).
- Symptom-directed physical examination pre-dose only
- Examination of injection site will be performed 1 hour (±30 min) pre-AGI-134 administration, 1 hour (±30 min) and 72 hours (±1 hour) post AGI-134 administration
- Vital signs (blood pressures, pulse rate, O2 saturation, oral temperature in °C, respiratory rate) will be assessed 1-hour pre-AGI-134 administration and 0.5, 1, 24, 36, 48 and 72 hrs post AGI-134 administration
- ECOG performance status
- Photography of superficial injected and non-injected lesions (if a different lesion is injected, the previous injected lesion should be photographed as well): 1 hour (±30 min) pre-AGI-134 administration and 1 hour (±30 min) and 72 hours (±1 hour) post AGI-134 administration
- Review general instructions before study drug administration (see section 5.7)

agalin A subsidiary of BIO		PRIVILEGED & CONFIDENTIAL
Investigational Product: AGI-134	A Phase I/IIa, multicentre, two-parts, open label study designed to evaluate the safety and tolerability of escalating	Protocol No. AGI-134.FIM.101
Phase: I/IIa	doses of AGI-134 in unresectable/metastatic solid tumours.	Version 6.1 31 May 2021

- AGI-134 administration (every effort should be made to inject the same lesion as in previous cycle)
- Blood will be drawn for:
  - PT/INR and aPTT (results should be available before injection)
  - o CBC with differential
  - Biochemistry panel
  - Blood for anti-Gal IgE pre-dose (if IgE anti-Gal is detected during assessment at Cycle 3, Cycle 4 dosing with AGI-134 will be cancelled)
  - o C5a pre-dose and 2 and 6 hours post AGI-134 administration
  - o Flow cytometry pre-dose and 24 hours post AGI-134 administration
  - o Cytokines pre-dose and 2, 6, 12 and 24 hours post AGI-134 administration
  - Anti-Gal antibodies IgG/IgM and sub classing pre-dose only
  - PBMC + cryopreservation pre-dose only
  - TCR Sequencing pre-dose only
  - RNA isolation (Gene expression/sequencing) 24 hours post AGI-134 administration

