Symptoms Directed Physical Examination		X	X 	X	X	X 	X	X	X 	X	X	X 	X	X			
Examination of injection sites			$X^5$	X	X	$X^5$	X	X	X 	X	X	X 	Х	X	X	X	
Vital Signs (blood pressures, pulse rate, O 2 sat., oral temperature (°C), respiratory rate)	Х		X 	X	X	X8	X	Х	X8	X	X	X 	X	Х		X	
Weight	X															X	
Height	X												T				
ECOG performance status	X		Х			X			X			X	T		X	X	
Photography pictures of lesions that are Superficial			X 	Х	Х	X 	X	X	X 	X	X	X 	X	X	X	X	
Review general instructions before study drug administration			X			X			X			X					
AGI-134 administration 			Х			X			Х			X	T				

		PRIVILEGED & CONFIDENTIAL
Investigational Product: AGI-134	A Phase I/IIa, multicentre, two-parts, open label study designed to evaluate the safety and tolerability of escalating doses of AGI-134 in unresectable/metastatic solid tumours.	Protocol No. AGI-134.FIM.101
Phase: I/IIa		Version 6.1 31 May 2021

Study Period:	Screening Phase	Baseline Assessments	3-Week Cycles								es				9-Week F.U Cycles	Termination Visit	Long-Term Follow-up				
Treatment Cycle:	Screening (Visit 1)	Pre-Dose	Cy	cle	1	C	ycle	2	C	ycle	3	Cy	Cycle 4		Cycle 4		Cycle 4		Weeks 18, 27, 36 & 45	Week 54 or early Termination	Survival Follow-up call
Days from injection (Safety assessment follow-up)	-28	0	1	8	15	1	8	15	1	8	15	1	8	15							
Scheduling Window (Days) unless specified otherwise	-28 to 0	-3 to 1 Pre- dose	8	+3			±3			±3			±3		±3	±3	Every 9 weeks (±7 days)				
Local Laboratory 							u														
Pregnancy Test – Serum or Urine 	X	X				X						X				X					
FSH screening for women who reported menopause less than two years.	X																				
Disease markers according to subject's disease	X					X						X									
HPV status for HNSCC 	X		П																		
PT/INR and aPTT	X	X				X			Х			X									
CBC with Differential	X	X	$X^{13}$	X	X	X			X			X				X					
Biochemistry Panel	X	X	$X^{13}$	X	X	X			X			X				X					
T3, free T4, and TSH	X					X						X				X					
HIV, HBV and HCV serology	X																				
Urinalysis	X	X				X						X									

agalin A subsidiary of BIG		PRIVILEGED & CONFIDENTIAL

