Post-study Anti-Cancer Therapy Status											X	X
Disease and Survival Status											X	X

agalin A subsidiary of BIG		PRIVILEGED & CONFIDENTIAL
Investigational Product: AGI-134	A Phase I/IIa, multicentre, two-parts, open label study designed to evaluate the safety and tolerability of escalating doses of AGI-134 in unresectable/metastatic solid tumours.	Protocol No. AGI-134.FIM.101
Phase: I/IIa		Version 6.1 31 May 2021

- Inclusion/Exclusion Criteria should be re-assessed at Baseline prior to final eligibility confirmation.
- A 12-lead ECG will be recorded at each cycle (1-4) prior to AGI-134 administration (up to 1 hour) and 2 hours after dose (±30 minutes). In Cycle 1 and 3, when a Holter device is connected, a printout should be extracted from the device at the appropriate timepoints.
- In Cycle 1 and 3, a 12-lead ECG Holter recording device will be connected to the subject 1-2 hours prior to AGI-134 administration and record ECG consecutively for at least 24 hours after 3. AGI-134 administration.
- To be performed up to 1 hour prior and 1 hour post AGI-134 administration
- To be performed 48-72 hours post AGI-134 administration (prior to tumour biopsy if applicable) 6.
- Vital signs will be collected up to 1 hour pre-dose and 0.5, 1, 24, 36, 48 and 72 hrs post AGI-134 administration Vital signs will be collected prior to AGI-134 administration and 2 hours post dose
- AGI-134 should be administered on Day 1 of each Cycle. Refer to "Administration AGI-134 and Tumour Biopsy Procedures in Study AGI-134.FIM.101" for detailed
- All laboratory assessment should be performed before investigational product administration, unless otherwise specified. Pregnancy test in Screening and Termination Visit must be serum. At other visits a urine test. 10.
- 11.
- HPV status assessment should be performed at local lab in case no available status from the time of diagnosis.
- To be drawn pre-dose and 24 hours post AGI-134 administration
- 14. To be drawn pre-dose and at 2,6,12, and 24 hours post AGI-134 administration
- To be drawn pre-dose and at 2 and 6 hours post AGI-134 administrations 15.
- To be drawn up to 1 hour prior to AGI-134 administration and 0.5, 1, 2, 4, 6, 8, 12, 24, 36, 48 and 72 hrs post AGI-134 administration 16.
- To be drawn up to 1 hour prior to AGI-134 administration and 2 hours post dose
- 18. To be drawn 24 hours post AGI-134 administration

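### Acute post-dose vital signs have no time in common between the intensive and sparse cycles, none is scheduled from 1 to 24 h after the first dose, and text and schedule tables conflict for Cycles 3 and 4

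*Combined protocol and SAP*

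**What the plan says.** **Vital signs, text.** Section 5.8.3 requires vital signs on Day 1 of Cycles 1 and 3 to be "measured up to 1 hour pre-AGI-134 administration and 0.5, 1, 24, 36, 48 and 72 hrs post dose". For the other two cycles it says: "On Cycle 2 Day 1 and Cycle 4 Day 1 will be measured pre-dose and 2 hours post dose". The cycle-by-cycle procedures in Sections 5.3.1 and 5.3.4 agree. Section 5.3.3 adds readings on Day 8 and Day 15 of Cycle 1; the text lists no such visits for later cycles.

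**Vital signs, tables.** Table 7 (Part 2) follows the text. Table 6 (Part 1) puts the intensive set at Cycles 1 and 4 and the 2 h set at Cycles 2 and 3. It also marks Day 8 and Day 15 in every cycle.

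**Other measurements.** Section 5.8.4 sets a local ECG before dosing and at 2 h in all four cycles. PK has a 2 h sample in all four cycles, in the text and in both tables. In Cycle 1 there are further PK draws at 4, 6, 8 and 12 h.

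**Injection site.** For Cycle 3, Section 5.3.4 asks for examination and photography before dosing and again "1 hour (±30 min) and 72 hours (±1 hour) post AGI-134 administration". Table 7 marks both Cycle 3 rows with footnote 6 alone: "To be performed 48-72 hours post AGI-134 administration (prior to tumour biopsy if applicable". Table 6 keeps the pre-dose and 1 h checks in all four cycles and adds 72 h in Cycles 1 and 4.

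**Analysis.** The synopsis says: "Changes in vital signs and routine laboratory data will be presented with descriptive statistics to demonstrate the trend of change". Section 8.2.2 specifies tables of changes from Baseline.

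**The concern.** Safety and tolerability are the primary endpoint of a first-in-human study in which each subject may receive four injections. A natural question is whether the immediate reaction changes on repeat exposure, and the plan shows interest in blood pressure around dosing (Section 5.7 on hypovolaemia and antihypertensives). If Cycle 1 is read at 0.5 and 1 h and Cycle 2 only at 2 h, a difference between them mixes the effect of the second dose with the effect of time since injection.

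The 1 to 24 h gap follows the first dose as well. In Part 1 a single subject per level can support escalation, and vital-sign findings reach the Safety Committee partly as adverse events. A short, symptomless change in blood pressure, temperature or saturation in that interval could go unrecorded.

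The text and table conflicts raise a second problem: sites in the two parts may collect different data in the same cycle.

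**Working it through.** No sample-size or power figure is involved. The check compares the scheduled times as sets.

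**Inputs.** Intensive set I = {0.5, 1, 24, 36, 48, 72} h. Sparse set S = {2} h.

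| Source | Cycle 1 | Cycle 2 | Cycle 3 | Cycle 4 | Day 8 and Day 15 |
|---|---|---|---|---|---|
| Sections 5.3 and 5.8.3 | I | S | I | S | Cycle 1 only |
| Table 7 (Part 2) | I | S | I | S | Cycle 1 only |
| Table 6 (Part 1) | I | S | S | I | every cycle |

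**Overlap of vital-sign times.**
- I ∩ S is empty, whichever cycles carry I.
- Text and Table 7: nothing is common to all four cycles. Cycles 1 and 3 share all six intensive times; Cycles 2 and 4 share 2 h.
- Table 6: Day 8 and Day 15 are common to all four cycles. Cycles 1 and 4 also share the six intensive times, and Cycles 2 and 3 also share 2 h.

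**Gap after the first dose.** The steps between consecutive times in I are 0.5, 23, 12, 12 and 24 h. The largest within the first 24 h is 24 − 1 = 23 h. It contains five scheduled PK draws (2, 4, 6, 8 and 12 h).

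**Pooling the parts.** Section 8.2 plans analyses of Parts 1 and 2 together. If each part follows its own table, Cycle 3 is S in Part 1 and I in Part 2, and Cycle 4 is the reverse. A pooled Cycle 3 or Cycle 4 summary would then have no Day 1 to Day 3 post-dose time common to both parts.

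**Effect of adding 2 h to I.** All four cycles then share {2} under every layout above. The largest first-day gap becomes 24 − 2 = 22 h. With 4, 6, 8 and 12 h also added, it becomes 24 − 12 = 12 h.

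**Injection-site times, Cycle 3.**

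| Source | Pre-dose | 1 h | Late check |
|---|---|---|---|
| Section 5.3.4 | yes | yes | 72 h ±1 h |
| Table 7 | no | no | 48-72 h |
| Table 6 | yes | yes | none (72 h is at Cycles 1 and 4) |

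The text and Table 6 therefore give a 1 h check in every cycle, and Table 7 does not. Footnote 6 also refers to a following biopsy. That fits Cycle 1 Day 3; Section 5.3.4 has the Cycle 3 biopsies taken before dosing.

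With about 35 Part 2 subjects, following Table 7 alone would cost at most about 35 × 1 = 35 examinations at 1 h and 35 × 2 = 70 photograph sets (pre-dose and 1 h). The loss is smaller for subjects who do not reach Cycle 3, and photographs apply only to superficial lesions.

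**The case against.** The strongest reply is that scheduled vital signs are only one part of the tolerability assessment. Section 5.8 also lists adverse events, dropouts due to them, ECG, physical examination and laboratory tests. Dose-limiting toxicities are defined by graded events or laboratory values, and significant vital-sign findings must be recorded as adverse events. Adverse-event recording and the 2 h ECG apply in every cycle. This stands. A reader might infer that tolerability cannot be compared across the four doses at all; the documents do not support that. If four doses is read as the four dose levels, the inference also fails, because every level follows the same schedule.

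The planned analysis is descriptive, with no between-cycle contrast, so no stated comparison is invalidated. That also stands. The weakness lies in what can be described, not in a test.

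The gap is not unobserved: in Cycle 1 a 12-lead Holter runs for at least 24 h, and unscheduled vital signs are allowed. But the Holter does not record blood pressure, temperature, saturation or respiratory rate, and unscheduled readings depend on someone seeing a reason to take them.

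A reader might use the monkey plasma figures in Section 1.1.1 to argue that most exposure falls inside the gap. Those are Day 29 values after subcutaneous or intravenous dosing. A share of plasma exposure does not show when an acute reaction follows an intratumoural injection, so they carry no weight here.

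A reader might also infer that Table 7 drops the Cycle 3 pre-dose injection-site examination. It does not in effect: the table keeps a pre-dose directed physical examination, and Section 5.8.5 has that examination inspect the injection site. The loss is confined to the 1 h examination and the pre-dose and 1 h photographs.

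**Conclusion.** The point holds in a limited form. Post-dose vital signs within the first 24 h cannot be compared at a matched time between intensive and sparse cycles, and none is scheduled for 23 h after the 1 h reading of the first dose. In Part 2 no scheduled post-dose vital-sign time is common to all four cycles. In Part 1 the common times are Day 8 and Day 15, and only if Table 6 is followed, because the text gives those visits for Cycle 1 alone.

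Two contradictions stand beside this. The intensive set is at Cycles 1 and 3 in Section 5.8.3 and Table 7 but at Cycles 1 and 4 in Table 6. The Cycle 3 injection-site and photography times differ between Section 5.3.4, Table 6 and Table 7. The stated loss for Part 2 assumes that sites work from Table 7 and not from the Cycle 3 text.

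The consequence is modest, but it determines which safety data exist at the end of the study, and missed readings cannot be recovered.

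**What to change.** 1. Add a vital-sign reading at the existing 2 h ECG and PK contact in the intensive cycles. All four cycles then share one acute time. Readings at the existing 4, 6, 8 and 12 h PK draws are optional and would shorten the gap further.
2. State in the analysis plan that the 2 h change from the same-day pre-dose value is tabulated by cycle. Section 5.2 lists no vital signs at the Baseline visit, so the reference value needs naming in any case.
3. Reconcile Sections 5.3.4 and 5.8.3 with Tables 6 and 7 on three matters: which cycles carry the intensive set, whether Day 8 and Day 15 readings apply after Cycle 1, and the Cycle 3 times and late window for injection-site examination and photography. The sponsor must decide which version applies.

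The cost is a few minutes of readings while the subject is already attending, slightly more data entry, and wording changes in Sections 5.3.1, 5.3.4 and 5.8.3 and Tables 6 and 7.
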